(PI: [name]; Co-PI: [name])

*Research and Analysis Plan (Revised 7/11/2022; Note: Original version of the plan was deposited on Open Science Framework website prior to start of study enrollment – see <https://osf.io/8ukfv/>)*

*Note: This 7.11.2022 update to our Research and Analysis plan adds an adjustment to impact analyses to take into account non-independence of youth nested within the same family (i.e., siblings) as siblings were randomized (see page 5). Because this adjustment is a more conservative approach, it was deemed appropriate to add despite the 18-month outcome analyses already being in progress. The modification is noted on page 11.*

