Random assignment will be conducted, following the survey assessments, at the individual level. The sample allocation ratio will be 3:1 in favor of the treatment group (i.e., three times as many assigned to the treatment as the control group). This ratio was selected for both pragmatic and scientific reasons. Pragmatically, affiliate buy-in to participate in the research will be greater if only a minority of youth are assigned to the control group and thus ineligible to receive services over the course of the study; also, with fewer youth assigned to the control group, there will be less need to reimburse affiliates for lost costs associated with intake procedures for youth who are assigned to the control group. Scientifically, a larger treatment group will provide enhanced opportunities for examining the implications that different combinations of treatment-related factors (e.g., mentor characteristics, relationship quality, match length) may have for program effectiveness (Dumville et al., 2006). Siblings within the same family that enroll in the study will be assigned randomly to treatment or control group in a yoked manner (i.e., using one random assignment envelope in the procedures described below).

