Generalized linear and nonlinear mixed-effects models (Bryk & Raudenbush, 1992; Fitzmaurice et al., 2004) will be used to test study hypotheses as these models can account for dependence among outcomes due to nesting of youth within both sites and families (i.e., siblings) as well as varying distributions of outcomes (e.g., binary, ordinal, continuous). Intercepts for sites and families within sites will be modeled as random and impact coefficients will be modeled as fixed. Covariates for tests of primary hypotheses will include youth demographics (i.e., age, gender, race/ethnicity, family structure, family income), baseline values of each primary outcome (i.e., history of court-related arrest pre-dating study enrollment, de-

linquent behavior, and substance use [presence or absence of substance use at baseline since recurring substance use was not assessed at baseline in the form it is being assessed at 4-year follow-up]), youth and parent reports of the youth's history, if any, of contacts with law enforcement not leading to arrest, and any other study measure of a potential contextual, behavioral, or attitudinal influence on criminal/delinquent behavior for which there is evidence of a non-negligible association with treatment/control group status (effect size of .05 or greater, per WWC standards, 2011). The same covariates will be used for tests of secondary hypotheses, with the addition of scores on the same measure or, where not available (as will be the case for some of the outcomes assessed at the 4-year follow-up for Secondary H3), the most closely related measure at baseline (i.e., strongest association), excluding those to be included as covariates in all analyses. Note that the analytic approach used will thus be ANCOVA (i.e., control for baseline scores on the outcome measures treated as a covariate) rather than a difference-in-differences approach (e.g., repeated-measures ANOVA).

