The multiple tests associated with primary hypotheses will be conducted using the Benjamini-Hochberg (1995) family-wise adjustment (advocated by the WWC) to control for Type I error with the false discovery rate set to .05. At 18 months, the court-related arrest outcome for the period 18 months following study enrollment will serve as the primary outcome for H1, along with the survey-based assessments of delinquent behavior and substance use for H2 and H3, respectively (i.e.,  $n = 4$  tests). At 4 years, the court-related arrest outcome for the period of 4 years following study enrollment, property- and violence-related delinquent behavior for the prior 2.5 years on the 4-year follow-up survey, and substance use for the prior 6-month period on the 4-year follow-up survey will supersede these outcomes as assessed at the 18-month follow-up for purposes of family-wise Type I error adjustment (i.e.,  $n = 4$  tests). Missing data patterns will be explored and addressed using multiple imputation (Rubin, 1987) as the assumption of ignorable missingness (i.e., missing at random) is reasonable in the context of the rich set of baseline covariate measures that will be available to model the probability of missingness. For the special case of participants with de-identified arrest data (H1), the missing indicator method will be used to accommodate missingness on baseline covariates, an approach which can be expected to yield unbiased results in the context of a randomized control trial (Groenwold et al., 2012). Analyses will adhere to prevailing sets of evidence standards, particularly those of WWC and the Society for Prevention Research (SPR, Flay et al., 2005; e.g., required tests for differential attrition), thus ensuring a high level of rigor. It should be noted that planned primary analyses will, in effect, weight each site proportional to the number of participants from that site.

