Estimation of power for the planned tests of program impact are based on the ultimate achieved sample size of approximately 1,350 youth, but are also dependent on a variety of considerations, some of which will be possible to determine only at the stage of data analysis. With this caveat, our estimates make allowance for nesting of data within sites, unequal size of the treatment and control groups, and across-site variation in participant numbers and conservatively assume a relatively high attrition rate of 20%, not taking into account some likely offset of power reductions due to attrition afforded by missing data imputation. For continuous outcomes (i.e., all measures examined in Secondary hypotheses H1, H2, and H3, except those assessed as dichotomous), our estimates indicate that power for tests of impact will be sufficient (.80 or greater) to detect a small treatment effect (Cohen's  $d = .18$  if we assume covariates account for 15% of the variance in the outcome and  $d = .17$  if we assume covariates account for 25% of the variance in the outcome). For binary outcomes (i.e., all outcomes for Primary hypotheses and outcomes assessed as dichotomous for Secondary hypotheses as specified above), assuming the same post-attrition sample size and taking into account unequal size of the treatment and control groups, there will be 80% power to detect the following illustrative population outcome differences between control and treatment groups, respectively: 5% vs. 1.9% (3.1% percentage point difference), 10% vs. 5.2% (4.8 percentage point difference), 20% vs. 12.8% (7.2 percentage point difference), 30% vs. 21.3% (8.7 percentage point difference), 40% vs. 30.5% (9.5 percentage point difference), and 50% vs. 40.2% (9.8 percentage point difference); power will necessarily be lower for those dichotomous outcomes examined in Secondary Hypothesis H3 (e.g., not being engaged in post-secondary education, training, or employment) that will not be applicable to the entire sample as indicated above. Because of a smaller than anticipated sample size, the study has less power than originally envisioned. A related consequence of the smaller sample size is that the number of participants with events (e.g., an arrest) in the tests of primary hypotheses (which all

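### The 80% power stated for the binary primary outcomes is at best a single-test figure: it leaves out the Benjamini-Hochberg rule and sibling clustering, and the 5% and 10% rows fall short even without them

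*Combined protocol and SAP*

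**What the plan says.** The power paragraph (Analysis section) starts from about 1,350 youth and assumes 20% attrition. For binary outcomes, covering all the primary hypotheses and the dichotomous secondary outcomes, it says "there will be 80% power to detect the following illustrative population outcome differences between control and treatment groups". The list begins "5% vs. 1.9% (3.1% percentage point difference), 10% vs. 5.2% (4.8 percentage point difference" and continues with 20% vs 12.8%, 30% vs 21.3%, 40% vs 30.5% and 50% vs 40.2%. On what was allowed for, it says "our estimates make allowance for nesting of data within sites, unequal size of the treatment and control groups, and across-site variation in participant numbers", together with the attrition. No significance level or sidedness is given.

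Elsewhere the plan sets two conditions that the power paragraph does not mention:

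- **Multiplicity.** In the Analysis section: "The multiple tests associated with primary hypotheses will be conducted using the Benjamini-Hochberg (1995) family-wise adjustment", "to control for Type I error with the false discovery rate set to .05". There are four primary tests at each time point.
- **Families.** Under randomization: "Siblings within the same family that enroll in the study will be assigned randomly to treatment or control group in a yoked manner". The July 2022 revision note says the update "adds an adjustment to impact analyses to take into account non-independence of youth nested within the same family", and the models now "account for dependence among outcomes due to nesting of youth within both sites and families".

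**The concern.** A power figure should describe the test that will decide the outcome. Here the primary outcomes are decided by BH over four tests, in a model with family intercepts. The listed allowances suggest a single unadjusted test with no family term. With no alpha or sidedness stated, a reader cannot see this.

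The arithmetic is also uneven. On the plan's own inputs the higher-rate rows come out near 80%, but the two lowest-rate rows do not. Those rows are likely to matter most for the arrest outcome, for which the plan itself expects a low base rate. If power there is well below 80%, a null arrest result says less than the plan implies.

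**Working it through.** **Inputs from the plan.** N = 1,350 × 0.80 = 1,080. The 3:1 allocation gives 270 control and 810 treated.

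**Step 1. Reproduce the stated figure.** The formula is the pooled two-proportion test: power = Φ[(d − z·s0)/s1]. Here d is the difference, s0 the pooled standard error under no difference, s1 the unpooled standard error, and z = 1.960 (two-sided .05, my inference).

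- 5% vs 1.9%: pooled rate (13.5 + 15.39)/1,080 = .02675; s0 = .01134; s1 = .01410. Power = Φ[(.031 − .02222)/.01410] = Φ(.622) = .733.
- 10% vs 5.2%: pooled rate .064; s0 = .01720; s1 = .01985. Power = Φ[(.048 − .03371)/.01985] = Φ(.720) = .764.

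The other four rows give .806, .819, .814 and .804. Exact binomial enumeration of the same test gives .732, .768, .807, .821, .815 and .803, so the shortfall is not caused by the normal approximation.

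Two-sided .05 is the best-fitting reading for two reasons. It reproduces the last four rows within 2 points. It also reproduces the plan's continuous-outcome figures with no multiplicity adjustment (d = .18 with 15% of variance explained: .793; d = .17 with 25%: .798).

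**Step 2. Try other methods on the 5% and 10% rows** (two-sided .05, same arms):

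| Method | 5% row | 10% row |
|---|---|---|
| Unpooled | .594 | .676 |
| Arcsine | .699 | .742 |
| Likelihood ratio | .701 | .747 |
| Log odds ratio | .749 | .783 |
| Pooled SE under both hypotheses | .781 | .797 |

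None reaches .80 for either row. One-sided .05 gives .81 and .84, and ignoring attrition gives .81 and .84, but each lifts the other four rows to .88–.89. Neither explains the list.

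**Step 3. Apply the BH rule** (m = 4, q = .05). The per-test threshold runs from .05/4 = .0125 to .05, so power depends on how many of the four effects are real. I simulated 200,000 sets of four independent binary outcomes. The real ones had the row's difference and the others were null at the control rate.

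| Control rate | Single test, .05 | Fixed .0125 | BH, 1 real | BH, 2 real | BH, 3 real | BH, 4 real |
|---|---|---|---|---|---|---|
| 5% | .73 | .58 | .58 | .62 | .66 | .70 |
| 10% | .76 | .60 | .60 | .66 | .71 | .74 |
| 20% | .81 | .65 | .65 | .71 | .75 | .79 |
| 30% | .82 | .66 | .66 | .72 | .77 | .80 |
| 40% | .81 | .64 | .65 | .71 | .76 | .79 |
| 50% | .80 | .63 | .63 | .70 | .74 | .78 |

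Starting instead from exactly 80% single-test power, BH gives .63, .69, .74 and .77 for one to four real effects. At correlation .5 between tests these become .62, .68, .73 and .76, so independence is not driving the result.

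**Step 4. Differences needed for 80% power** (percentage points, pooled formula):

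| Control rate | Stated | Needed at .05 | Needed at .0125 |
|---|---|---|---|
| 5% | 3.1 | 3.3 | 3.7 |
| 10% | 4.8 | 5.0 | 5.7 |
| 20% | 7.2 | 7.1 | 8.3 |
| 30% | 8.7 | 8.5 | 10.0 |
| 40% | 9.5 | 9.3 | 11.0 |
| 50% | 9.8 | 9.8 | 11.6 |

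**Step 5. Siblings.** The documents give no sibling share or intraclass correlation (ICC). For sibling pairs the design effect is 1 + share × ICC. Assuming a share of .10 to .20 and an ICC of .2 to .5, it runs from 1 + .10 × .2 = 1.02 to 1 + .20 × .5 = 1.10. That costs about 1 to 4 points at .05 and 1 to 5 points at .0125.

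**The case against.** - **The method may simply be unnamed.** With the pooled standard error under both hypotheses, all six rows lie within about 3 points of 80% (.781, .797, .827, .832, .821, .805). The list could come from a rough approximation of that kind. This is a fair reason to let the authors name their method. It does not rescue the figures, because exact enumeration still gives .732 and .768.
- **The check uses an unstratified test.** The plan says it allowed for sites, but gives no site variance, so its exact basis cannot be rebuilt. This limit stands.
- **The correction to the two rows is about 0.2 points, and the 20% to 40% rows err slightly the other way.** True. The larger issue is the gap between single-test power and power under BH.
- **BH has no single power, and an unadjusted figure suits the secondary outcomes on the same list.** Both true. If all four effects are real, as hypothesised, the loss is about 2 to 4 points; the 58 to 66% range assumes three are null. But the paragraph presents the list as covering the primary outcomes too, and does not say it is unadjusted.
- **Offsets exist.** The plan calls 20% attrition conservative, counts no gain from imputation, and adjusts for baseline outcomes. An efficiency gain equivalent to 15% explained variance (N/.85) would give .79 to .87 at .05 and .65 to .74 at .0125. The plan claims no such gain for binary outcomes, and its sensitivity section warns of possible precision loss with standard covariate adjustment.
- **Few siblings may be enrolled**, since a youth whose sibling is already a participant is ineligible. This supports treating the sibling loss as small.
- **General caveats are given.** The plan admits lower power than envisioned and few events. Neither caveat mentions BH or families.

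**Conclusion.** The concern holds. As written, 80% is at best the power of one unadjusted two-sided .05 test, and the 5% and 10% rows do not reach it even then (about 73% and 76%). Under the rule that decides the primary outcomes, power across the rows is 58 to 66% with one real effect and 70 to 80% with all four. The .0125 figures are a floor, not the power the design delivers.

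These results assume 270 and 810 analysed youth, an inferred two-sided .05, no site variance and no covariate gain. The BH figures by row also assume independent outcomes with equal effects. The sibling loss rests wholly on assumed inputs and is secondary. The documents state no arrest rate, so linking arrest to the lowest rows is inference from the plan's expectation of low base rates. The planned analysis remains valid; it is the stated power that needs correcting.

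**What to change.** In the power paragraph:

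1. State alpha, sidedness and the formula or software method.
2. Label the existing list as unadjusted, single-test power.
3. Correct the 5% and 10% rows to about 3.3 and 5.0 points for 80% at two-sided .05, or document the method that gave 3.1 and 4.8.
4. For the primary outcomes, report power or detectable differences under BH as a range from the .0125 threshold to .05, and show the case where all four effects are real.
5. Add a family design effect from the observed share of enrolled siblings, with the assumed ICC stated.
6. Say whether any covariate gain is assumed for binary outcomes.

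The cost is a short recalculation and one reworded paragraph. Sample size, model and decision rule are unchanged. The only drawback is less favourable stated figures.

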involve dichotomous measures) will be smaller; with relatively low base rates already anticipated for some outcomes (e.g., arrest), the small number of events has the potential to introduce instability/imprecision into tests of program impact (i.e., regression coefficients could be biased in both positive and negative directions; see, e.g., Peduzzi et al., 1996, and Vittinghoff & McCulloch, 2007). (Note from an earlier version of this plan, prior to the decision to pursue a longer-term follow-up via the 4-year assessment: In part, to help address this concern, we may pursue longer-term follow-up so that the cumulative rates of key events (e.g., arrest) are higher, yielding more precise and stable estimates of program impact. In this case, the later follow-ups will supersede the earlier ones as primary.)

Primary study analyses will be supplemented with sensitivity analyses to determine the robustness of the findings obtained to varying assumptions and analytic approaches. These include: 1) modeling the program impact coefficient in each analysis as a random effect; 2) use of an alternative estimator (PLEASE) in analyses involving binary outcomes because of the potential for some loss of precision when adjusting impact estimates for covariates using a standard estimation approach (Colantuoni & Rosenblum, 2015); 3) using case deletion to account for missing data on outcomes and regression models that control for all potential variables related to the probability of missingness; 4) weighting of observations based on the extent to which study youth enrolled at each site are representative of youth served by BBBSA nationally in its CBM program; 5) weighting of observations by the inverse probability of availability of follow-up survey and/or arrest records data as a check on potential bias introduced by study attrition (Kosse et al., 2016); 6) treating primary outcomes (e.g., delinquent behavior) as continuous/multi-categorical rather than binary; 7) analyses using the undifferentiated measure of involvement in delinquent behavior that was examined for potential impacts with a portion of the sample prior to determining the final measures of delinquent behavior; and 8) where the same outcome measure is available at each of the 3 times of assessment, testing for program impact on change across all 3 time points using longitudinal growth models with growth modelled to reflect change over actual time (i.e., 0, 1.5, and 4 for baseline, 18 months, and 4 years).

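### Two of the six binary power rows fall short of the stated 80%: 5% vs 1.9% has about 73% power and 10% vs 5.2% about 76%, assuming a two-sided .05 test

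*Combined protocol and SAP*

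**What the plan says.** The power paragraph of the Analysis section starts from the "ultimate achieved sample size of approximately 1,350 youth" and says the estimates "conservatively assume a relatively high attrition rate of 20" per cent. For binary outcomes it proceeds by "assuming the same post-attrition sample size and taking into account unequal size of the treatment and control groups", and then states without qualification that "there will be 80% power to detect the following illustrative population outcome differences between control and treatment groups, respectively". Six pairs follow. The first two are "5% vs. 1.9% (3.1% percentage point difference), 10% vs. 5.2% (4.8 percentage point difference"; the other four are 20% vs 12.8%, 30% vs 21.3%, 40% vs 30.5% and 50% vs 40.2%.

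Two other places supply inputs. The random assignment text says "The sample allocation ratio will be 3:1 in favor of the treatment group". The multiplicity text applies a Benjamini-Hochberg procedure to the primary tests "to control for Type I error with the false discovery rate set to .05". That is the only error rate in the plan; no significance level, sidedness or test is named for the power figures.

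**The concern.** The six rows share one sample size and one claimed power, so a single calculation should return about 80% for each. Under the usual two-proportion calculation, four do and the two with the lowest event rates do not.

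All primary outcomes are binary, and the plan says it is working "with relatively low base rates already anticipated for some outcomes (e.g., arrest"). The 5% and 10% rows are therefore the ones a reader would consult for a low-rate outcome. Someone interpreting a null result there would take the chance of missing the stated difference to be 20%, when it is about 27% or 24%. The plan gives no expected arrest rate, so the link to Primary H1 is possible rather than established.

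**Working it through.** **Inputs.** Enrolled about 1,350 and attrition 20% (power paragraph): 1,350 × 0.80 = 1,080. Allocation 3:1 (random assignment text): n_C = 270, n_T = 810. Two-sided alpha of .05 is my assumption, so z = 1.960; for 80% power z = 0.842.

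**Testing the assumption on the plan's own effect sizes.** For a continuous outcome with covariate R², the detectable effect is d = (1.960 + 0.842) × √[(1 − R²)(1/270 + 1/810)].

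- R² = .15: d = .182 (plan: .18)
- R² = .25: d = .170 (plan: .17)

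One-sided .05 would give .161 and .151, which do not match.

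**Binary rows.** With p̄ = (270 p_C + 810 p_T)/1,080, s₀ = √[p̄(1 − p̄)(1/270 + 1/810)] and s₁ = √[p_C(1 − p_C)/270 + p_T(1 − p_T)/810], power = Φ[(p_C − p_T − 1.960 s₀)/s₁].

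- 5% vs 1.9%: p̄ = .02675, s₀ = .01134, s₁ = .01410. (.031 − 1.960 × .01134)/.01410 = 0.62, so power = .733.
- 10% vs 5.2%: p̄ = .0640, s₀ = .01720, s₁ = .01985. (.048 − 1.960 × .01720)/.01985 = 0.72, so power = .764.

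All six rows, by method, at 270/810 and two-sided .05:

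| Method | 5% | 10% | 20% | 30% | 40% | 50% |
|---|---|---|---|---|---|---|
| Pooled z (formula above) | .733 | .764 | .806 | .819 | .814 | .804 |
| Pearson test, exact enumeration | .732 | .768 | .807 | .821 | .815 | .803 |
| Wald log-odds, exact enumeration | .731 | .761 | .805 | .818 | .813 | .802 |
| Likelihood ratio, exact enumeration | .701 | .747 | .796 | .813 | .811 | .801 |
| Arcsine | .699 | .742 | .795 | .812 | .809 | .802 |
| Unpooled z | .594 | .676 | .759 | .792 | .800 | .800 |
| Null variance only | .781 | .797 | .827 | .832 | .821 | .805 |

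No method puts the 5% row at 80%. The 10% row comes close only under the null-variance approximation, which overstates the enumerated Pearson power of .768.

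**What 80% would take.** Keeping the printed rates, the pooled formula reaches .80 at a total of about 1,306 for the 5% row and 1,192 for the 10% row. That means attrition of at most 1 − 1,306/1,350 = 3% and 1 − 1,192/1,350 = 12%. Keeping 1,080, the treatment rate must be 1.67% (exact Pearson 1.69%) and 5.00% (5.03%).

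**Expected events at 1,080.** 5% row: 270 × .05 = 13.5 plus 810 × .019 = 15.4, about 29. 10% row: 27.0 plus 42.1, about 69.

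**Sensitivity to attrition (0, 5, 10, 15, 20%), pooled.** 5% row: .811, .794, .775, .755, .733. 10% row: .843, .826, .807, .786, .764. Using the 1,356 of the Overview in place of 1,350 gives .735 and .766.

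**The case against.** The strongest objection is that the result depends on a test the plan never names. The hypotheses are directional, and one-sided .05 lifts the two rows to .81 and .84. But it also puts the other four at .88 to .89 and misses the plan's effect sizes. Assuming no attrition behaves the same way (.81 and .84, with the others at .88 to .89) and contradicts the stated post-attrition basis. The null-variance formula, solved for 80%, gives treatment rates of 1.85% and 5.19%, near the printed 1.9% and 5.2%. For the other rows, however, it gives 13.0%, 21.6%, 30.7% and 40.3%, against the printed 12.8%, 21.3%, 30.5% and 40.2%. No single method tried returns all six. What stands is that the second decimal depends on the method and that the source of the discrepancy is unknown.

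A second objection is that the plan allows for nesting within sites, which the check does not model. An ordinary design effect would lower power, as would a threshold stricter than .05 under the multiplicity procedure. Covariate adjustment could raise it, but none is stated for the binary rows.

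Third, the plan calls the rows illustrative, admits reduced power and warns about small numbers of events, while enrolment is complete and the 18-month analyses are under way. This is fair on consequence and is why the point is modest. It does not make a definite 80% statement correct for two rows that do not meet it.

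**Conclusion.** The point holds. At 270 control and 810 treatment, with two-sided .05 assumed, 5% vs 1.9% has about 73% power and 10% vs 5.2% about 76%, while the other four rows meet the claim. Across the other two-sided .05 methods tried, the two rows range over .59 to .78 and .68 to .80, and exact enumeration does not support the top of either range. These are unadjusted benchmarks, before covariate gain, clustering by site or family, or multiplicity. The practical effect is small: about 0.2 percentage points in each detectable difference, with no change to sample size or decision rule. It is still a wrong figure that should be corrected.

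**What to change.** Choose one of two corrections to the sentence.

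- Restate the rows as about 5% vs 1.7% (3.3 points) and 10% vs 5.0% (5.0 points). The 1.7% is the solved 1.67% rounded to one decimal, with power .792 pooled and .797 exact; 10% vs 5.0% gives .800 and .806. If the first row must not fall below 80% at one decimal, 1.6% gives .818 and .827.
- Keep the printed rates and state about 73% and 76% power for those two rows.

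Either way, add a clause naming the test, alpha and sidedness behind all six rows. If the authors used a different method, stating it would let a reader check the list. The cost is two figures and one clause in one sentence; the only downside is a slightly less favourable stated figure.
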